14.1 Adverse Event Summaries

All AEs will be coded using the MedDRA Version 23.0. A treatment-emergent adverse event (TEAE) is defined as any event that has an onset date on or after the first dose of study drug. All AEs collected in the eCRFs will be presented in data listings, but only TEAEs will be summarized in data tables. An overall summary will be presented that includes the number of TEAEs and the number and percentage of subjects who experienced at least one TEAE, by treatment group. This summary will also include breakdowns of TEAEs further categorized as (for ocular and non-ocular separately, where appropriate):

- Ocular TEAEs
- Non-ocular TEAEs
- Ocular Non-Serious TEAEs
- Non-ocular Non-Serious TEAEs
- Most Frequent (> 5% in any arm) Ocular TEAEs
- Most Frequent (> 5% in any arm) Non-ocular TEAEs
- Expected TEAEs
- Unexpected TEAEs
- Suspected treatment-related TEAEs
- All SAEs
- Suspected treatment-related SAEs
- Not Suspected treatment-related SAEs

- TEAEs leading to study discontinuation
- TEAEs by maximal severity
- Suspected Treatment-Related Ocular TEAEs by maximal severity
- Suspected Treatment-Related Non-ocular TEAEs by maximal severity
- Not Suspected Treatment-Related Ocular TEAEs by maximal severity
- Not Suspected Treatment-Related Non-ocular TEAEs by maximal severity

Separate summaries (for ocular and non-ocular, where appropriate) will also be provided for these categories of TEAEs by SOC and PT. If a subject reports the same PT multiple times within the same SOC, that PT will only be reported once within that SOC. As with the PT, if a subject reports multiple conditions within the same SOC, that SOC will only be reported once. In the summary, SOC will be listed in ascending alphabetical order; PTs will be listed in order of descending frequency for CSF-1 treated subjects within each SOC.

All AEs will be presented in a subject listing, with ocular AEs listed separately from non-ocular AEs. All TEAEs leading to study discontinuation will be listed separately. In addition, all SAEs will be presented in a separate listing.

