10.8 Safety Analysis

Verbatim descriptions of AEs will be mapped to Medical Dictionary for Regulatory Activities (MedDRA) terms and be presented in a data listing. Treatment Emergent AEs (TEAEs), those that occur after the first dose of study drug, will be summarized by treatment group using frequency and percent for each System Organ Class (SOC) and Preferred Term (PT) within each SOC. Similar summaries will also be presented for serious TEAEs, TEAEs leading to death, TEAEs leading to study drug discontinuation, TEAEs related to IP and TEAEs by severity. When reporting the incidence of AEs, a subject will only be counted once if they ever experience an event within the SOC and ever experience the individual PT within the SOC.

Actual results and changes from baseline results in monocular and binocular BCVA at 4m and Low- Luminance BCVA, slit-lamp biomicroscopy, conjunctival redness grading, IP drop comfort, IOP, and dilated fundus examination will be summarized descriptively at each visit by treatment group.

Full details of the safety analyses will be specified in the formal SAP.

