AE	Adverse Event
ATC	Anatomical Therapeutic Chemical
BCVA	Best Corrected Visual Acuity
BDCVA	Best Distance-Corrected Visual Acuity
BID	Twice Daily
CI	Confidence Interval
eCRF	Electronic Case Report Form
ETDRS	Early Treatment of Diabetic Retinopathy Study
FAS	Full Analysis Set
GEE	Generalized Estimating Equation
ICF	Informed Consent Form
ICH	International Council for Harmonisation
IMDF	Imputing Missing Data as Failures
IOP	Intraocular Pressure
IP	Investigational Product
IRT	Interactive Response Technology
HIPAA	Health Information Portability and Accountability Act
LDPE	Low-Density Polyethylene
LL-BDCVA	Low-Luminance Best Distance-Corrected Visual Acuity
logMAR	Logarithm of the Minimum Angle of Resolution
LS	Least Square
MCMC	Markov Chain Monte Carlo
MedDRA	Medical Dictionary for Regulatory Activities
MI	Multiple Imputation
NCS	Not Clinically Significant
ODO	Observed Data Only
PPS	Per Protocol Set
PT	Preferred Term
SAE	Serious Adverse Event
SAF	Safety Set
SAP	Statistical Analysis Plan
SD	Standard Deviation
SDC	Statistics & Data Corporation
SOC	System Organ Class
TEAE	Treatment-Emergent Adverse Event
TPA	Tipping Point Analysis
VA	Visual Acuity
WHO	World Health Organization

1. Introduction

The purpose of this statistical analysis plan (SAP) is to describe the planned analyses and reporting for the Orasis 20-150-0003 protocol, Version 2.0 (Amendment 1), dated 07Jan2021 (NEAR-2 study).

This Version 2.0 SAP replaces the previous finalized and signed Version 1.0 SAP, dated 22Nov2021.

This SAP is being written with due consideration of the recommendations outlined in the most recent International Council for Harmonisation (ICH) E9 Guideline entitled Guidance for Industry: Statistical Principles for Clinical Trials and the most recent ICH E3 Guideline entitled Guidance for Industry: Structure and Content of Clinical Study Reports.

This SAP describes the data that will be analyzed and the subject characteristics, efficacy, and safety assessments that will be evaluated. This SAP provides details of the specific statistical methods that will be used. The statistical analysis methods presented in this document will supersede the statistical analysis methods described in the clinical protocol. Any additional analyses required to supplement the planned analyses described in this SAP will be duly noted in the clinical study report.

2. Study Objectives

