The primary objective of this study is to evaluate the efficacy of CSF-1 (0.4% pilocarpine hydrochloride ophthalmic solution) for the temporary correction of presbyopia.

The secondary objectives of this study are to evaluate the safety and tolerability of CSF-1 versus Vehicle.

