8.5 Adjustment for Multiplicity

If the primary null hypothesis, H_{01} , is rejected at a 2-sided alpha = 0.05 in favor of CSF-1 in the alternative hypothesis, H_{11} , tested as delineated in the primary efficacy analysis section ([Section 12.1](#)), then the study will be considered a success and the following key secondary hypotheses will be tested in hierarchical order, each at a 2-sided alpha = 0.05, where inference will be made on each null hypothesis only if the prior null hypotheses are rejected in favor of CSF-1.

1. Visit 3 (Day 8), 2 hours following Dose 1 (H_{02})
2. Visit 3 (Day 8), 1 hour following Dose 2 (H_{03})
3. Visit 3 (Day 8), 2 hours following Dose 2 (H_{04})

9. Disposition of Subjects

Subject disposition will be presented in terms of the numbers and percentages of subjects who were randomized, completed the study, and discontinued from the study. A discontinued subject is someone who does not complete the 4 protocol-defined study visits. Subjects who are not discontinued from the study will be considered study completers. Disposition will be summarized by treatment arm for all randomized subjects. The reasons for study discontinuation will also be summarized and include: AE, lost to follow-up, physician decision, protocol violation, study terminated by sponsor, withdrawal by subject, death, and other. A subject listing will be provided which includes the date and reason for study discontinuation.

The number of subjects in each of the analysis sets (FAS, PPS, and SAF) will be displayed by treatment arm, with the number of subjects and percentages calculated using randomized subjects as the denominator. The number and percentage of subjects with any (major, or minor) protocol deviations will be summarized by treatment arm and overall for all randomized subjects. Protocol deviations will be classified as major or minor prior to the closure of the database during a masked review of each protocol deviation. Major deviations will be defined as those deviations that potentially affect the analysis of the primary study endpoint.

A subject listing will be provided which includes the date of the deviation, the deviation code and description, and the classification of whether the deviation was deemed major or minor. In addition, subject listings will include treatment arm and ICF signature date, and exclusions from the PPS. There will also be a listing of screen failures.

10. Demographic and Baseline Characteristics

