12.1 Primary and Key Secondary Efficacy Analysis

The primary efficacy endpoint in this study is the percentage of subjects with a ≥ 3 -line (15-letter) gain, from baseline, in best distance-corrected visual acuity (BDCVA) at 40 cm (Precision Vision chart) and no loss in BDCVA ≥ 5 letters (ETDRS chart) at Visit 3, 1 hour following Dose 1 in the study eye. The key secondary efficacy endpoints are defined the same as the primary efficacy endpoint, except for being measured at 2 hours following Dose 1, 1 hour following Dose 2, and 2 hours following Dose 2, all at Visit 3.

The primary and key secondary efficacy analysis will be conducted in the FAS with missing data handled in the following manners:

1. Discontinuation of study drug and non-optimal compliance will be ignored [treatment policy strategy].
2. Withdrawal due to lack of efficacy or AEs: missing data will be singly imputed as failure [hypothetical strategy].
3. Missing data without withdrawal or withdrawal due to reasons other than lack of efficacy or AEs: missing data will be imputed employing Multiple Imputation (MI) using randomized treatment-based Markov Chain Monte Carlo (MCMC) methods.

No subject data will be excluded from the FAS due to protocol violations/deviations. The multiple imputation of missing values will be completed for the continuous measures (BDCVA at 40 cm and BDCVA at 4 m), then the response variable will be determined therefrom. Imputation of failure due to lack of efficacy or AE will be assigned after multiple imputation is performed.

Variables for treatment group, baseline for BDCVA at 40 cm and baseline for BDCVA at 4 m will also be included in the multiple imputation model. 25 complete imputed datasets will be created.

Example SAS® code for the multiple imputation:

```
PROC MI DATA=DATAIN OUT=MI NIMPUTE=25 SEED=118787 minimum=-0.3 maximum=1;
  MCMC INITIAL=EM;
  VAR TRTPN VA40 VA40BL VA4 VA4BL;
RUN;
```

Where TRTPN = treatment group, coded 1 for CSF-1, else 0

VA40 = value of BDCVA at 40 cm for Visit 3, 1 hour after Dose 1

VA40BL = baseline value of BDCVA at 40 cm

VA4 = value of BDCVA at 4 m for Visit 3, 1 hour after Dose 1

VA4BL = baseline value of BDCVA at 4 m

For each imputed dataset, a logistic regression model with baseline BDCVA at 40 cm as a covariate and treatment as a main effect will be used to obtain the treatment effect estimate, odds ratio, and 95% confidence interval (CI) for odds ratio.

Example SAS® code for the logistic model is shown here:

```

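### SAP 14.1 reports adverse events that led to leaving the study but not, as Protocol 10.8 plans, those that led to stopping study drug

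*SAP*

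**What the plan says.** Protocol 10.8 lists the TEAE summaries to be produced in addition to the one by System Organ Class (SOC) and Preferred Term (PT). After serious TEAEs it names "TEAEs leading to death, TEAEs leading to study drug discontinuation, TEAEs related to IP and TEAEs by severity". It closes by handing the detail on: "Full details of the safety analyses will be specified in the formal SAP".

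The categories in SAP 14.1 include TEAEs that led to discontinuing the study. None refers to discontinuing the drug. The listing follows the same line: "All TEAEs leading to study discontinuation will be listed separately". Section 1 of the SAP settles which document governs: "The statistical analysis methods presented in this document will supersede the statistical analysis methods described in the clinical protocol".

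Two other parts of the SAP show what the terms mean. Section 9 defines study discontinuation by visits: "A discontinued subject is someone who does not complete the 4 protocol-defined study visits". Section 12.1, item 1, deals with stopping the drug: "Discontinuation of study drug and non-optimal compliance will be ignored [treatment policy strategy". Withdrawal because of lack of efficacy or an adverse event is a separate item with a different rule.

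The objective at issue is in SAP section 2: "The secondary objectives of this study are to evaluate the safety and tolerability of CSF-1 versus Vehicle".

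**The concern.** The number of subjects per arm who stop a treatment because of an adverse event is a standard description of tolerability, and tolerability is part of this trial's secondary objective. The protocol planned that description. The SAP puts a neighbouring quantity in its place, and the visible text gives no reason. Because the SAP supersedes the protocol, the protocol's category does not survive by default.

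The primary analysis adds a second reason to want the count. It ignores stopping of study drug under a treatment policy strategy, so a reader of the report will want to know how often adverse events caused that stopping in each arm. The visible SAP has no output that answers this.

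**Working it through.** No figure in the plan needs reproducing here. The check is a comparison of definitions, followed by an illustration of size.

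**Step 1: are the two categories the same?** Under SAP section 9 a subject is discontinued if the four visits are not completed; stopping the drops plays no part in that definition. SAP 12.1 gives stopping the drug and withdrawing separate rules. Protocol 5.3 says that subjects may be withdrawn for an adverse event, so withdrawal is possible but not automatic. The plan therefore allows for a subject who stops the drug and stays.

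**Step 2: where does each kind of subject appear?**

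| Subject | Protocol 10.8, stopped drug | SAP 14.1, left study (summary and listing) | SAP 9, reasons for leaving study | Other TEAE tables and AE listings |
|---|---|---|---|---|
| Stops drops for a TEAE and leaves the study because of it | yes | yes | yes | yes |
| Stops drops for a TEAE and completes all four visits | yes | no | no | yes |

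The second row is the gap. The last column limits it. SAP 14.1 reports "the number and percentage of subjects who experienced at least one TEAE, by treatment group", and breaks TEAEs down by ocular or non-ocular site, expectedness, suspected relation to treatment, maximal severity, and SOC and PT. These tables use the safety set, which includes everyone who received at least one dose. SAP 14.5 also summarises drop comfort.

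**Step 3: how large could the gap be?** The documents give no rate of stopping drug for a TEAE while staying in the study. Take an assumed rate r and the planned 150 subjects per arm (Protocol 10.5, SAP section 5):

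subjects not identified per arm = 150 × r

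- r = 1%: 150 × 0.01 = 1.5
- r = 3%: 150 × 0.03 = 4.5
- r = 5%: 150 × 0.05 = 7.5

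These values of r are illustrative and have no source in the documents.

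**Step 4: can the missing category be produced?** Protocol 9.1 requires the action taken to be documented for each adverse event. If the case report form records a change to study drug in that item, no new data are needed.

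**The case against.** Four arguments can be made for leaving the SAP as it is.

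- **The protocol defers to the SAP on safety detail.** It does, but Protocol 10.8 names this summary itself. Dropping a named output is a change from the protocol, and SAP section 16 exists to record such changes.
- **The omission cannot be fully confirmed.** SAP sections 16, 19 and 20, and the table of changes in section 18, show no content in the available text. A drug-discontinuation table, or a reason for dropping it, could be there. This stands, and the point is limited to the visible text. If such a table exists, the wording of 14.1 still needs to agree with it.
- **Stopping drug and leaving the study may nearly coincide.** Visits 3 and 4 are built around staff-instilled doses and timed assessments after them, and no follow-up off drug is described. This stands as an argument about size: the gap may be close to zero. It does not make the categories equal, because SAP 12.1 provides for the case.
- **The table could be added at reporting.** SAP section 1 allows supplementary analyses noted in the clinical study report. That is true, but this output was already planned and should not depend on a later choice.

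A reader might also infer that these subjects disappear from the tolerability results, or that the reported discontinuation rate is biased low, mainly in the CSF-1 arm. The documents support none of this. The subjects' TEAEs stay in every other table and listing, and their comfort scores are summarised wherever assessed. A table of events that led to leaving the study is correct for what its label says; the plan lacks a second table. No rates by arm are given, so nothing shows that the gap would fall on one arm more than the other.

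**Conclusion.** The point holds as a mismatch between protocol and SAP that removes one planned tolerability output. If SAP 14.1 is followed as written, the number and percentage per arm who stopped study drug because of a TEAE are not reported, and subjects who stop for that reason but complete the four visits are not identified in any visible discontinuation output. The size of the gap and any difference between arms are unknown; the range of 1.5 to 7.5 subjects per arm rests wholly on the assumed 1% to 5%. Primary and key secondary inference, sample size and trial conduct are unaffected. The conclusion assumes that the SAP contents not visible here do not already supply the table. It is best treated as a free improvement.

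**What to change.** Add TEAEs leading to study drug discontinuation to SAP 14.1 beside the existing study-discontinuation category. Summarise it by arm and by SOC and PT, separately for ocular and non-ocular events, with a subject listing. Derive it from the action-taken item in Protocol 9.1, and confirm first that the case report form records stopping of study drug there. If the omission was intended, record it with its reason in SAP section 16.

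The cost is one more table and one more listing from data that the protocol already requires.

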14.2 Best Distance-Corrected Visual Acuity

Safety variables include BDCVA at 4 m under normal and low-luminance testing conditions.

Monocular BDCVA summaries will specify study eye and fellow eye. Monocular BDCVA and Low-Luminance BDCVA (LL-BDCVA) at 4 m will be measured at pre-treatment, post-Dose 1 and post-Dose 2 as mentioned in the schedule of assessments ([Section 3.2](#)). The observed BDCVA as well as the change from baseline in BDCVA and LL-BDCVA will be summarized by treatment group using continuous descriptive summary statistics, and subject-specific BDCVA and LL-BDCVA data will also be presented in a listing for each visual range, separately. Tables will also provide the number and percentage of eyes that lose 10 or more letters BCDVA at 4 m.

14.3 Slit-Lamp Biomicroscopy Examination

A slit-lamp biomicroscopy examination of the eyelid, conjunctiva, cornea, anterior chamber, iris, and lens will be conducted on both eyes at all scheduled visits pre-treatment, and an End of Visit slit lamp will also be completed at Visit 1 (Day -14 to -1), Visit 2 (Day 1), Visit 3 (Day 8), and Visit 4 (Day 15). Magnification will be consistent with the investigator's standard clinical practice. The subject will be seated for the examination. The results will be graded as normal, abnormal not clinically significant (NCS), or abnormal clinically significant (CS). A table will summarize the findings with frequency counts and percentages for each treatment group at each timepoint and for each eye (study eye and fellow eye). Percentages will be based on the number of subjects in each treatment group with responses. A subject listing of the slit-lamp parameters will also be produced.

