Current presbyopia treatment strategies include corrective lenses with single vision or bifocal/multifocal lenses, corneal refractive surgery, corneal inlay procedures, and intra-ocular lens surgery. Monovision correction improves the near vision of one eye (through the use of lenses, contacts, or surgery) while allowing the other eye to be used for distance vision. This approach has had variable results and may cause disturbances in depth-perception (Fernandez, Schwarz et al. 2013). Lastly, surgical correction of vision in presbyopia includes conductive keratoplasty, laser-assisted in-situ keratomileusis (LASIK), laser-assisted epithelial keratomileusis (LASEK), photorefractive keratectomy (PRK), corneal inlays, and accommodative or multifocal intraocular lenses (IOLs). The results of these procedures are variable, at times inconsistent, and contraindicated in some patient groups (Moussa, Jehangir et al. 2017). The inconsistencies regarding the success of some of these procedures of presbyopia treatment indicate a need for alternative strategies.

The treatment proposed here repurposes a muscarinic receptor agonist to stimulate effects on iris and ciliary contractility via stimulation of muscarinic acetylcholine receptor M3. Pilocarpine, a muscarinic agonist, has been successful in treating cases of dilated pupil following ocular surgery (Patel, Jenkins et al. 2002) and a broad spectrum of systemic conditions including botulism (Monaco, Freddi et al. 1998), leprosy (Lana-Peixoto, Campos et al. 2014), sarcoidosis (Bowie and Givre 2003), and Ross syndrome (Weller, Wilhelm et al. 1992, Chemmanam, Pandian et al. 2007).

CSF-1 was initially developed as a combination of a Non-Steroidal Anti-Inflammatory Drug (NSAID), diclofenac, with pilocarpine to reduce a potential inflammatory response associated with pilocarpine.

The safety and efficacy of CSF-1 (the initial combination and current formulation) is well established based on several previous clinical studies; an investigator-led feasibility study and two Phase 2a studies demonstrated favorable safety and preliminary efficacy.

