14.7 Dilated Indirect Fundoscopy

Dilated indirect fundoscopy will be performed at Visit 1 (Day -14 to -1) and Visit 4 (Day 15) using indirect ophthalmoscope. Dilated indirect fundoscopy should always be performed after IOP and all other ocular examinations.

Dilated Indirect fundoscopy parameters collected for the left and right eyes include, vitreous, retina, macula, choroid, and optic nerve. Each parameter is rated "Normal," "Abnormal (NCS)," or "Abnormal (CS)." The subject listing of dilated indirect fundoscopy will include all ratings collected for each parameter in both eyes and the investigator's findings associated with each parameter at each timepoint.

15. Interim Analyses

An interim analysis is not planned for this study.

16. Changes from Protocol-Stated Analyses

17. References

[figure not shown]
US Federal Register. (1998) International Conference on Harmonization; Guidance for Industry: Statistical Principles for Clinical Trials. Department of Health and Human Services: Food and Drug Administration. Federal Register, Vol. 63, No. 179, September 16, 1998, page 49583. (E9)

US Federal Register. (1996) International Conference on Harmonization; Guidance for Industry: Structure and Content of Clinical Study Reports. Department of Health and Human Services: Food and Drug Administration. Federal Register Vol. 61, July 17, 1996, page 37320. (E3)

18. Revision History

[figure not shown]
This SAP v2.0 amendment was issued following SAP v1.0, issued on 22NOV2021.

[figure not shown]
Table 2. Summary of Changes from SAP v. 1.0

[figure not shown]

[figure not shown]
19. Tables

Tables that will be included in the **topline** delivery are shown in **boldface** font.

[figure not shown]

[figure not shown]

20. Listings

21. Figures

Figures may be produced at the discretion of the study sponsor.

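### SAP 14.3 and 14.7 specify no baseline-to-post-dose summary of slit-lamp or fundus findings, so newly abnormal or worsened eyes are not counted by arm

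*SAP*

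**What the plan says.** Protocol 10.8 covers the ocular safety examinations in one sentence. It opens with "Actual results and changes from baseline results in monocular and binocular BCVA at 4m" and ends with "slit-lamp biomicroscopy, conjunctival redness grading, IP drop comfort, IOP, and dilated fundus examination will be summarized descriptively at each visit by treatment group". Slit lamp and dilated fundus examination are therefore both within the scope of results and changes from baseline. The section then defers: "Full details of the safety analyses will be specified in the formal SAP". The SAP Introduction gives the SAP precedence: "The statistical analysis methods presented in this document will supersede the statistical analysis methods described in the clinical protocol".

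SAP 14.3 grades six structures (eyelid, conjunctiva, cornea, anterior chamber, iris, lens) as normal, abnormal not clinically significant (NCS) or abnormal clinically significant (CS). The output is a frequency table, "A table will summarize the findings with frequency counts and percentages for each treatment group at each timepoint and for each eye", and a listing. No change, shift or new-abnormality output is named.

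SAP 14.7 grades vitreous, retina, macula, choroid and optic nerve on the same three categories at Visits 1 and 4. The only output it describes is a listing: "The subject listing of dilated indirect fundoscopy will include all ratings collected for each parameter in both eyes". SAP 10.2 also places baseline funduscopy in listings only. The opening paragraph of SAP Section 14, however, includes fundoscopy among the measures to be summarised descriptively by arm and visit, as appropriate.

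By contrast, the SAP writes out change from baseline for distance acuity (14.2), conjunctival redness (14.4) and intraocular pressure (14.6).

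**The concern.** Safety and tolerability are the secondary objectives of the trial. For an examination graded in ordered categories, the useful safety question is how many eyes got worse after dosing, by arm. A frequency table at each time point gives the number of eyes in each grade, not the number that moved. Eyes that newly become abnormal can be offset by eyes whose baseline finding resolves. Separate tables by visit also do not give the number of eyes that worsened at any time.

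The Protocol Introduction makes these examinations relevant. Diclofenac was originally included "to reduce a potential inflammatory response associated with pilocarpine", and the current formulation omits it. For the fundus the problem is different: SAP 14.7 specifies no between-arm table, and it does not match the opening of its own Section 14.

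**Working it through.** The plan states no figure on this point, so there is none to reproduce. The check is a comparison of texts, followed by an illustration with assumed counts.

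**Text comparison**

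| Examination | Protocol 10.8 | SAP subsection | SAP Section 14 opening |
|---|---|---|---|
| Slit lamp | Results and change from baseline, by visit and arm | 14.3: frequencies by arm, time point and eye; listing | Descriptive summary, as appropriate |
| Dilated fundus | Results and change from baseline, by visit and arm | 14.7: listing only | Descriptive summary, as appropriate |

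The change-from-baseline element appears in no readable SAP text for either examination.

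**One arm, slit lamp**

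Input from the documents: about 150 subjects per arm (SAP Section 5), hence 150 study eyes. Assumed, because the documents give no rates: 9 eyes abnormal for a given structure before dosing, 5 resolved, 5 new.

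- Abnormal after = abnormal before − resolved + new = 9 − 5 + 5 = 9.
- Frequency table: 9/150 = 6.0% before and 9/150 = 6.0% after.
- Shift table: 150 − 9 = 141 eyes normal at baseline; 5/141 = 3.5% newly abnormal.

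**Range of assumptions**

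The count stays the same whenever new = resolved. With 150 eyes:

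| Abnormal at baseline | New eyes leaving the count unchanged, if a quarter resolve (% of baseline-normal eyes) | The same, if half resolve |
|---|---|---|
| 5% (7.5 eyes) | 1.9 (1.3%) | 3.75 (2.6%) |
| 10% (15 eyes) | 3.75 (2.8%) | 7.5 (5.6%) |
| 20% (30 eyes) | 7.5 (6.25%) | 15 (12.5%) |
| 30% (45 eyes) | 11.25 (10.7%) | 22.5 (21.4%) |

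**Two arms**

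The planned table is also by arm, so the vehicle column matters. Take the same 9 abnormal eyes of 150 at baseline in each arm, with 5 new and 5 resolved on CSF-1 and no new findings on vehicle.

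- If vehicle also has 5 resolved: 9 − 5 = 4, and 4/150 = 2.7% against 6.0% on CSF-1. The excess of 5 eyes is visible.
- If vehicle has none resolved: 9/150 = 6.0% against 6.0%. The 5 new eyes on CSF-1 are not visible.

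Concealment between arms therefore needs unequal resolution rates or unequal baselines, by chance or otherwise. Even in the first case the reader sees a net difference and not how many eyes changed.

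**Which grades are affected**

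Protocol 5.2 excludes subjects with clinically significant slit-lamp or fundus findings at Visit 1. Baseline CS counts should therefore be about zero, and a later CS count is in effect a count of new findings. Offsetting is essentially confined to movement between normal and NCS.

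**Examinations after the first dose**

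SAP 14.3 gives five slit-lamp examinations after the first dose: Visit 2 end of visit, and pre-treatment and end of visit at each of Visits 3 and 4. No planned output combines them into eyes that ever worsened.

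**The case against.** The case against giving this weight is substantial.

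- Clinically relevant deterioration must be recorded as an adverse event (Protocol 9.1), and ocular events are tabulated by arm, relatedness and maximal severity (SAP 14.1). This stands for important findings. It depends on an investigator's judgement, eye by eye, and a move from normal to NCS may never become an event.
- Conjunctival redness has its own graded scale with change from baseline (SAP 14.4), active ocular inflammation at Visits 2 to 4 is a withdrawal criterion (Protocol 5.3), and discontinuation reasons are summarised by arm. The Phase 2b study also found that diclofenac did not significantly improve tolerability or safety. The slit lamp is therefore not the only check on inflammation. This stands.
- The randomised vehicle arm exposes many drug excesses in the planned table, as shown above. This stands, subject to similar baselines and resolution.
- Full listings are produced. They allow the count to be made by hand but do not present it by arm.
- The contents of SAP Section 16 (changes from the protocol) and Section 19 (tables) cannot be read here. A shift table may be listed there. This stands and makes the request conditional.

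A reader might infer that Protocol 10.8 already plans shift tables. It does not. It defines change as a subtraction, which has no direct meaning for Normal/NCS/CS. Its omnibus sentence also includes drop comfort, which SAP 14.5 scores only from instillation onwards. The detail is left to the SAP. What the protocol supports is that some summary of change was intended for both examinations.

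**Conclusion.** The point holds as a modest gap in descriptive safety reporting. SAP 14.3 as readable gives no count of newly abnormal or worsened eyes, SAP 14.7 does not match the opening of Section 14, and neither carries over the change from baseline that Protocol 10.8 names. In the illustration the missing information is 5 of 141 eyes (3.5%) behind an unchanged 6.0%. The rates are assumptions, and the size moves with them across the range shown.

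Three stronger readings are tempting and are not supported. First, that fundus abnormalities could cancel out: 14.7 describes no frequency table in which they could, so the gap there is the unspecified summary. Second, that the sponsor has removed the fundus summary: the Section 14 opening still promises one, so this is an inconsistency. Third, that the slit-lamp table could look worse with no new findings: for the same 150 eyes, the abnormal count cannot exceed its baseline value unless an eye newly becomes abnormal.

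Nothing here touches alpha, power or the primary analysis.

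**What to change.** In SAP 14.3, keep the frequency table and add, by arm and by eye (study and fellow), a shift table for each structure from the Visit 2 pre-treatment grade to the worst post-dose grade (Normal/NCS/CS). Include the number and percentage of eyes that are newly abnormal or worsened.

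In SAP 14.7, reconcile the text with the opening of Section 14 by adding a Visit 1 to Visit 4 shift table, by arm and eye, for each of the five fundus parameters. SAP 8.3 already allows Visit 1 as baseline when no Visit 2 measurement exists, so no new baseline definition is needed.

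If Section 19 already lists such tables, a cross-reference from 14.3 and 14.7 is enough.

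The cost is two or three extra descriptive tables from data already collected. There is no new procedure, and no protocol amendment is needed because Protocol 10.8 leaves the detail of the safety analyses to the SAP.
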